#### 11.3.4 Response Review

All brain MRI scans will be reviewed centrally by the DF/HCC Tumor Imaging Metrics Core (TIMC). CNS response will be assessed centrally using the criteria outlined in Section 11.0.

### 11.4 **Antitumor Effect – Extracranial lesion assessments**

For patients that have metastatic meningioma, participants should be re-evaluated for extracranial response every 6 weeks. In addition to a baseline scan, confirmatory scans should also be obtained 6 weeks following initial documentation of objective response.

Response and progression will be evaluated in this study using the new international criteria proposed by the Response Evaluation Criteria in Solid Tumors (RECIST) guideline (version 1.1) [*Eur J Ca* 45:228-247, 2009]. Changes in the largest diameter (unidimensional measurement) of the tumor lesions and the shortest diameter in the case of malignant lymph nodes are used in the RECIST criteria.

#### 11.4.1 Definitions

Evaluable for Target Disease response. Only those participants who have measurable disease present at baseline, have received at least one cycle of therapy, and have had their disease re-evaluated will be considered evaluable for target disease response. These participants will have their response classified according to the definitions stated below. (Note: Participants who exhibit objective disease progression prior to the end of cycle 1 will also be considered evaluable.)

Evaluable Non-Target Disease Response. Participants who have lesions present at baseline that are evaluable but do not meet the definitions of measurable disease, have received at least one cycle of therapy, and have had their disease re-evaluated will be considered evaluable for non-target disease. The response assessment is based on the presence, absence, or unequivocal progression of the lesions.

#### 11.4.2 Disease Parameters

Measurable disease. Measurable lesions are defined as those that can be accurately measured in at least one dimension (longest diameter to be recorded) as  $\geq 20$  mm by chest x-ray or  $\geq 10$  mm with CT scan, MRI, or calipers by clinical exam. All tumor measurements must be recorded in millimeters (or decimal fractions of centimeters).

Malignant lymph nodes. To be considered pathologically enlarged and measurable, a lymph node must be  $\geq 15$  mm in short axis when assessed by CT scan (CT scan slice thickness recommended to be no greater than 5 mm). At baseline and in follow-up, only the short axis will be measured and followed.

Non-measurable disease. All other lesions (or sites of disease), including small lesions (longest diameter  $< 10$  mm or pathological lymph nodes with  $\geq 10$  to  $< 15$  mm short axis), are considered non-measurable disease. Bone lesions, leptomeningeal disease, ascites, pleural/pericardial effusions, lymphangitis cutis/pulmonitis, inflammatory breast disease, abdominal masses (not followed by CT or MRI), and cystic lesions are all considered non-measurable.

Note: Cystic lesions that meet the criteria for radiographically defined simple cysts should not be considered as malignant lesions (neither measurable nor non-measurable) since they are, by definition, simple cysts.

‘Cystic lesions’ thought to represent cystic metastases can be considered as measurable lesions, if they meet the definition of measurability described above. However, if non-cystic lesions are present in the same participant, these are preferred for selection as target lesions.

Target lesions. All measurable lesions up to a maximum of 2 lesions per organ and 5 lesions in total, representative of all involved organs, should be identified as **target lesions** and recorded and measured at baseline. Target lesions should be selected on the basis of their size (lesions with the longest diameter), be representative of all involved organs, but in addition should be those that lend themselves to reproducible repeated measurements. It may be the case that, on occasion, the largest lesion does not lend itself to reproducible measurement in which circumstance the next largest lesion which can be measured reproducibly should be selected. A sum of the diameters (longest for non-nodal lesions, short axis for nodal lesions) for all target lesions will be calculated and reported as the baseline sum diameters. If lymph nodes are to be included in the sum, then only the short axis is added into the sum. The baseline sum diameters will be used as reference to further characterize any objective tumor regression in the measurable dimension of the disease.

Non-target lesions. All other lesions (or sites of disease) including any measurable lesions over and above the 5 target lesions should be identified as **non-target lesions** and should also be recorded at baseline. Measurements of these lesions are not required, but the presence, absence, or in rare cases unequivocal progression of each should be noted throughout follow up.

### 11.4.3 Methods for Evaluation of Disease

All measurements should be taken and recorded in metric notation using a ruler, calipers, or a digital measurement tool. All baseline evaluations should be performed as closely as possible to the beginning of treatment and never more than 3 weeks before the beginning of the treatment.

The same method of assessment and the same technique should be used to characterize each identified and reported lesion at baseline and during follow-up. Imaging-based evaluation is preferred to evaluation by clinical examination unless the lesion(s) being followed cannot be imaged but are assessable by clinical exam.

Clinical lesions. Clinical lesions will only be considered measurable when they are superficial (*e.g.*, skin nodules and palpable lymph nodes) and  $\geq 10$  mm in diameter as assessed using calipers (*e.g.*, skin nodules). In the case of skin lesions, documentation by color photography, including a ruler to estimate the size of the lesion, is recommended.

Chest x-ray. Lesions on chest x-ray are acceptable as measurable lesions when they are clearly defined and surrounded by aerated lung; however, CT is preferable.

Conventional CT and MRI. This guideline has defined measurability of lesions on CT scan based on the assumption that CT thickness is 5mm or less. If CT scans have slice thickness greater than 5 mm, the minimum size of a measurable lesion should be twice the slice thickness. MRI is also acceptable in certain situations (*e.g.* for body scans).

Use of MRI remains a complex issue. MRI has excellent contrast, spatial, and temporal resolution; however, there are many image acquisition variables involved in MRI, which greatly impact image quality, lesion conspicuity, and measurement. Furthermore, the availability of MRI is variable globally. As with CT, if an MRI is performed, the technical specifications of the scanning sequences used should be optimized for the evaluation of the type and site of disease. Furthermore, as with CT, the modality used at follow-up should be the same as was used at baseline and the lesions should be measured/assessed on the same pulse sequence. It is beyond the scope of the RECIST guidelines to prescribe specific MRI pulse sequence parameters for all scanners, body parts, and diseases. Ideally, the same type of scanner should be used and the image acquisition protocol should be followed as closely as possible to prior scans. Body scans should be performed with breath-hold scanning techniques, if possible.

### 11.4.4 Response Criteria

#### 11.4.4.1 Evaluation of Target Lesions

Complete Response (CR): Disappearance of all target lesions. Any pathological lymph nodes (whether target or non-target) must have reduction in short axis to  $< 10$  mm.

Partial Response (PR): At least a 30% decrease in the sum of the diameters of target lesions, taking as reference the baseline sum diameters.

Progressive Disease (PD): At least a 20% increase in the sum of the diameters of target lesions, taking as reference the smallest sum on study (this includes the baseline sum if that is the smallest on study). In addition to the relative increase of 20%, the sum must also demonstrate an absolute increase of at least 5 mm. (Note: the appearance of one or more new lesions is also considered progressions).

Stable Disease (SD): Neither sufficient shrinkage to qualify for PR nor sufficient increase to qualify for PD, taking as reference the smallest sum diameters while on study.

#### 11.4.4.2 Evaluation of Non-Target Lesions

Complete Response (CR): Disappearance of all non-target lesions and normalization of tumor marker level. All lymph nodes must be non-pathological in size (<10 mm short axis).

Note: If tumor markers are initially above the upper normal limit, they must normalize for a patient to be considered in complete clinical response.

Non-CR/Non-PD: Persistence of one or more non-target lesion(s) and/or maintenance of tumor marker level above the normal limits.

Progressive Disease (PD): Appearance of one or more new lesions and/or *unequivocal progression* of existing non-target lesions. *Unequivocal progression* should not normally trump target lesion status. It must be representative of overall disease status change, not a single lesion increase.

Although a clear progression of “non-target” lesions only is exceptional, the opinion of the treating physician should prevail in such circumstances, and the progression status should be confirmed at a later time by the review panel (or Principal Investigator).

#### 11.4.4.3 Evaluation of New Lesions

The finding of a new lesion should be unequivocal (i.e. not due to difference in scanning technique, imaging modality, or findings thought to represent something other than tumor (for example, some ‘new’ bone lesions may be simply healing or flare of pre-existing lesions). However, a lesion identified on a follow-up scan in an anatomical location that was not scanned at baseline is considered new and will indicate PD. If a new lesion is equivocal (because of small size etc.), follow-up evaluation will clarify if it truly represents new disease and if PD is confirmed, progression should be declared using the date of the initial scan on which the lesion was discovered.

#### 11.4.4.4 Evaluation of Best Overall Response

The best overall response is the best response recorded from the start of the treatment until disease progression/recurrence (taking as reference for progressive disease the smallest measurements recorded since the treatment started). The patient's best response assignment will depend on the achievement of both measurement and confirmation criteria.

#### For Participants with Measurable Disease (i.e., Target Disease)

Target Lesions	Non-Target Lesions	New Lesions	Overall Response	Best Overall Response when Confirmation is Required*
CR	CR	No	CR	≥4 wks Confirmation**
CR	Non-CR/Non-PD	No	PR	≥4 wks Confirmation**
CR	Not evaluated	No	PR	
PR	Non-CR/Non-PD/not evaluated	No	PR	
SD	Non-CR/Non-PD/not evaluated	No	SD	Documented at least once ≥4 wks from baseline**
PD	Any	Yes or No	PD	no prior SD, PR or CR
Any	PD***	Yes or No	PD	
Any	Any	Yes	PD	

* See RECIST 1.1 manuscript for further details on what is evidence of a new lesion.            ** Only for non-randomized trials with response as primary endpoint.            *** In exceptional circumstances, unequivocal progression in non-target lesions may be accepted as disease progression.
 
Note: Participants with a global deterioration of health status requiring discontinuation of treatment without objective evidence of disease progression at that time should be reported as “symptomatic deterioration.” Every effort should be made to document the objective progression even after discontinuation of treatment.
				

#### For Participants with Non-Measurable Disease (i.e., Non-Target Disease)

Non-Target Lesions	New Lesions	Overall Response
CR	No	CR
Non-CR/non-PD	No	Non-CR/non-PD*
Not all evaluated	No	not evaluated
Unequivocal PD	Yes or No	PD
Any	Yes	PD
* ‘Non-CR/non-PD’ is preferred over ‘stable disease’ for non-target disease since SD is		

increasingly used as an endpoint for assessment of efficacy in some trials so to assign this category when no lesions can be measured is not advised

#### 11.4.5 Duration of Response

Duration of overall response: The duration of overall response is measured from the time measurement criteria are met for CR or PR (whichever is first recorded) until the first date that recurrent or progressive disease is objectively documented (taking as reference for progressive disease the smallest measurements recorded since the treatment started, or death due to any cause. Participants without events reported are censored at the last disease evaluation).

Duration of overall complete response: The duration of overall CR is measured from the time measurement criteria are first met for CR until the first date that progressive disease is objectively documented, or death due to any cause. Participants without events reported are censored at the last disease evaluation.

Duration of stable disease: Stable disease is measured from the start of the treatment until the criteria for progression are met, taking as reference the smallest measurements recorded since the treatment started, including the baseline measurements.

#### 11.4.6 Progression-Free Survival

Overall Survival: Overall Survival (OS) is defined as the time from randomization (or registration) to death due to any cause, or censored at date last known alive.

Progression-Free Survival: Progression-Free Survival (PFS) is defined as the time from randomization (or registration) to the earlier of progression or death due to any cause. Participants alive without disease progression are censored at date of last disease evaluation.

Time to Progression: Time to Progression (TTP) is defined as the time from randomization (or registration) to progression, or censored at date of last disease evaluation for those without progression reported.

#### 11.4.7 Response Review

All non-CNS scans will be reviewed centrally by the DF/HCC Tumor Imaging Metrics Core (TIMC).

## **12. END OF TREATMENT/INTERVENTION**

### **12.1 Duration of Treatment**

#### **12.1.1 CR, PR, or SD**

Patients who are in CR, PR or SD will continue on therapy until progression of disease, excessive toxicity requiring the patient to come off of treatment, or the patient withdraws from treatment. After treatment is discontinued, patients will be followed per the study calendar in section 10.0.

#### **12.1.2 Disease Progression**

Remove from protocol therapy any patient with disease progression. Document details, including tumor measurements, on data forms.

After disease progression, patients should be followed for survival per the study calendar (Section 10.0).

#### **12.1.3 Discontinuation of study agent**

If the patient discontinues study agent, patients should be followed for disease progression and survival per the study calendar (Section 10.0).

### **12.2 Definitions and Follow-up Requirements**

Definition of ineligible patients: A study participant who is registered to the trial but does not meet all of the eligibility criteria is deemed to be ineligible. Patients who are deemed ineligible may continue protocol treatment, provided the treating physician, study chair, and executive officer agree there are no safety concerns if the patient were to continue protocol treatment. Notification of the local IRB may be necessary per local IRB policies.

Definition of clinical follow-up: The follow-up period where the study participant is no longer receiving treatment, but is still following the study calendar for tests, exams, and correlative endpoints (e.g., specimen collection, quality of life, disease assessments as required by the study).

Definition of survival only follow-up: The follow-up period where the study participant is monitored for long-term endpoints, is no longer receiving study treatment, and is not required to follow the study calendar for tests, exams, and correlative endpoints (e.g. specimen collection, quality of life, disease assessments as required by the study). In this follow-up period, there is a schedule in which case report forms should be submitted, but the physician visits are based on the standard of care.

#### **12.2.1 Follow-up for Ineligible Patients**

Study participants who are registered to the trial but deemed ineligible must complete follow-up requirements as specified below.

Baseline, on-study and off-treatment notice data submission required.

#### **12.2.2 Follow-up for Patients Never Receiving Protocol Intervention**

Study participants who are registered to the trial but who never go on to receive study intervention must still complete follow-up requirements as specified below.

Baseline, on-study and off-treatment notice data submission required.

### **12.3 Extraordinary Medical Circumstances**

If, at any time the constraints of this protocol are detrimental to the patient's health and/or the patient no longer wishes to continue protocol therapy, protocol therapy shall be discontinued. In this event:

Document the reason(s) for discontinuation of therapy on data forms.

Follow the patient for protocol endpoints as required by the Study Calendar.

## **13.0 STATISTICAL CONSIDERATIONS**

### **13.1 Study Design**

There will be a single phase 2 arm in this study. Patients with recurrent or residual meningioma will be eligible for this trial. There is no planned interim analysis.

### **13.2 Endpoints**

#### **Primary Endpoints:**

The primary endpoint is progression-free survival at 6 months (PFS6). PFS6 is defined as not having progressive disease or death within six months of the first day of treatment. Contrast-enhanced cranial magnetic resonance imaging (MRI) will be performed every 6 weeks. Standard response criteria will be used (see [Section 11.0](#)).

All patients meeting the eligibility criteria that have signed the consent form and have begun treatment will be considered evaluable for the analysis of primary endpoint.

#### **Secondary Endpoints:**

1. Toxicity by CTCAE criteria (grade 3 or higher hematologic toxicity; grade 3 or higher neurologic toxicity)
2. Overall survival
3. Intracranial response as defined by RANO criteria

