### 1.3 Secondary Objectives

1. To determine the toxicity of pembrolizumab in patients with recurrent high-grade meningioma (WHO grade II atypical meningioma and WHO grade III anaplastic meningioma)
2. To estimate the overall survival of patients with recurrent high-grade meningioma receiving pembrolizumab
3. To estimate the response rate of patients with recurrent high grade meningioma receiving pembrolizumab

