  - For **Grade 2** events, treat with corticosteroids.
  - For **Grade 3-4** events, treat with systemic corticosteroids.
  - When symptoms improve to Grade 1 or less, steroid taper should be started and continued over no less than 4 weeks.
- **Cerebral Edema**

Due to the immunologic nature of pembrolizumab administration, cerebral edema could theoretically result as a consequence of pembrolizumab administration due to immune infiltration of the brain. Symptoms related to cerebral edema may include headache or neurologic deficit that is either new or worsened. Patients with any signs or symptoms of cerebral edema should be treated as clinically appropriate including initiation or increased systemic corticosteroid dosing, treatment with an osmotic diuretic or surgical decompression. Subsequent pembrolizumab dosing should be immediately interrupted if significant clinical symptoms attributable to cerebral edema develop. Treatment with additional pembrolizumab doses may only be re-initiated if clinically significant symptoms attributable to cerebral edema have resolved to grade  $\leq 1$  or pre-treatment baseline. Patients who develop CTCAE 4.0 grade-4 cerebral edema attributable to pembrolizumab administration should not receive further pembrolizumab doses and should discontinue study therapy.

Recommendations to manage irAEs not detailed elsewhere in the protocol are detailed in Table 4.

Table 4 Dose Modification and Toxicity Management Guidelines for Immune-related AEs Associated with Pembrolizumab

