Myocarditis	Grade 1 or 2	Withhold	
 
Based on severity of AE administer corticosteroids
 
	
 
Ensure adequate evaluation to confirm etiology and/or exclude other causes
 

	Grade 3 or 4	Permanently discontinue		
All other immune-related AEs	Intolerable/persistent Grade 2	Withhold	
 
Based on type and severity of AE administer corticosteroids
 
	
 
Ensure adequate evaluation to confirm etiology and/or exclude other causes
 

	Grade 3	Withhold or discontinue based on the type of event. Events that require discontinuation include and not limited to: Guillain-Barre		

		Syndrome, encephalitis		
	Grade 4 or recurrent Grade 3	Permanently discontinue		

1. Withhold or permanently discontinue pembrolizumab is at the discretion of the investigator or treating physician.
 
NOTE:          For participants with Grade 3 or 4 immune-related endocrinopathy where withhold of pembrolizumab is required, pembrolizumab may be resumed when AE resolves to <math>\leq</math> Grade 2 and is controlled with hormonal replacement therapy or achieved metabolic control (in case of T1DM).
				

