### **13.7 Analysis of Secondary Endpoints**

Safety and Tolerability: All adverse events recorded during the trial will be summarized for all patients having received one or more doses of pembrolizumab. The proportions of patients with grade-3 or higher hematologic toxicities or grade-3 or higher neurologic toxicities will be presented with 90% exact binomial confidence intervals. The incidence of events that are new or worsening from the time of first dose of treatment will be summarized according to system organ class and/or preferred term, severity (based on CTCAE grade), type of adverse event, and relation to study treatment. Deaths reportable as SAEs and non-fatal serious adverse events will be listed by patient and tabulated by primary system organ class, and type of adverse event.

Overall Survival: The distributions of overall survival will be summarized using the method of Kaplan-Meier. The follow-up of patients who are alive at the time of analysis will be censored at the date of last assessment of vital status. Median OS will be presented and accompanied by 90% confidence intervals estimated using log(-log(survival)) methodology. Survival point estimates at 3 and 6 months will also be presented with confidence intervals.

Intracranial/Extracranial Response: Contrast-enhanced cranial magnetic resonance imaging (MRI) will be performed every 6 weeks. The proportion of patients with intracranial response (CR, PR or SD by RANO) will be presented with a two-sided, 90% exact binomial confidence interval.

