## **13.9 Reporting and Exclusions**

### **13.9.1 Evaluation of Toxicity**

All participants who have received at least one dose of study medication will be evaluable for toxicity from the time of their first treatment.

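### Do Sections 13.2 and 13.7 need an overall grade 3+ toxicity proportion, with its own confidence interval, to serve the toxicity objective?

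*Combined protocol and SAP*

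**What the plan says.** Secondary objective 1 (Section 1.3) is broad: "To determine the toxicity of pembrolizumab in patients with recurrent high-grade meningioma". Section 13.2 turns it into a two-part endpoint: "Toxicity by CTCAE criteria (grade 3 or higher hematologic toxicity; grade 3 or higher neurologic toxicity". Section 13.7 attaches precision to the same two parts: "The proportions of patients with grade-3 or higher hematologic toxicities or grade-3 or higher neurologic toxicities will be presented with 90% exact binomial confidence intervals".

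Section 13.7 does not stop there. It opens by committing to summarize all recorded adverse events in every patient who received at least one dose. It then says that the incidence of events new or worsening since first dose "will be summarized according to system organ class and/or preferred term, severity (based on CTCAE grade), type of adverse event, and relation to study treatment". Reportable deaths and non-fatal serious events are also listed patient by patient and tabulated by organ class. Section 13.9.1 fixes the denominator: "All participants who have received at least one dose of study medication will be evaluable for toxicity from the time of their first treatment".

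On expected toxicity, Section 5.5 contains Table 4, titled "Dose Modification and Toxicity Management Guidelines for Immune-related AEs Associated with Pembrolizumab". It has nine named event rows and an open row for all other immune-related events. Section 5.5 also warns that "cerebral edema could theoretically result as a consequence of pembrolizumab administration due to immune infiltration of the brain".

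**The concern.** The objective is general and the named endpoint is narrow. The nine named rows of Table 4 are pneumonitis, diarrhea/colitis, liver enzyme or bilirubin elevation, diabetes/hyperglycemia, hypophysitis, hyperthyroidism, hypothyroidism, nephritis and myocarditis. None is hematologic or neurologic. On this reading, the only toxicity figures with an interval miss most of the toxicity that the protocol spends its management sections on. They also carry no attribution condition.

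The practical worry is about the published report. Organ-class rows cannot be added up, because one patient may appear in several. If a paper printed only those rows, a reader could not recover how many patients had at least one severe event. If it led with the two named proportions, both might be low while severe immune-related events sat in a descriptive table without an interval.

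**Working it through.** **1. Does the primary decision depend on this?** Section 13.6 gives n = 24, success at 10 or more, null 26%, alternative 52%, one-sided 0.1 and power of at least 88%.

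- Type I error = P(X ≥ 10 | n = 24, p = 0.26) = 0.0692, within 0.1.
- Power = P(X ≥ 10 | n = 24, p = 0.52) = 0.8884, which reproduces the stated figure.

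No toxicity quantity enters either calculation. Section 13.5 has no interim monitoring plan, and no section sets a statistical toxicity threshold or a toxicity-based sample size. A further toxicity interval would therefore feed no rule.

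**2. Are the ingredients of the overall proportion already in the plan?**

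| Ingredient | Where it is provided |
|---|---|
| Denominator | 13.9.1 and 13.7: at least one dose |
| Grade | 13.7 (CTCAE); Section 7.5 |
| Relation to treatment | 13.7; scales in Section 7.7 and Table 6 |
| Onset rule | 13.7: new or worsening since first dose |
| Collection period | Section 10, footnote l: all events to the 30-day visit; serious events and events of clinical interest to 90 days |
| Interval method | 13.7: 90% exact binomial |

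The trial team has everything it needs to count patients with at least one grade 3+ event, from any cause or related.

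**3. How much could a reader be left guessing if the row were not printed?** The documents give no toxicity rates, so the counts here are assumed. Suppose organ-class rows show 2, 2 and 1 patients with a grade 3+ related event.

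- Fewest patients (full overlap) = max(2, 2, 1) = 2.
- Most patients (no overlap) = 2 + 2 + 1 = 5.

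The exact two-sided 90% interval for x of n runs from the 5% quantile of Beta(x, n − x + 1) to the 95% quantile of Beta(x + 1, n − x). Section 13.3 gives n = 26 accrued and 24 evaluable.

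| n | 2 patients | 5 patients |
|---|---|---|
| 26 | 7.7% (1.4% to 22.3%) | 19.2% (7.9% to 36.3%) |
| 24 | 8.3% (1.5% to 24.0%) | 20.8% (8.6% to 38.9%) |

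The ambiguity would be real, but it arises only if the report omits the overall count. Once that count is printed, anyone can compute the interval from x and n.

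**4. Could the named endpoint read as spotless?** For 0 of 26, the 90% upper limit is 1 − 0.05^(1/26) = 10.9%. The chance of a zero is (1 − p)^26, where p is an assumed any-cause rate for the two classes combined: 59% at p = 2%, 26% at 5%, 6.5% at 10% and 0.3% at 20%. A zero is possible, but the full adverse event summary by grade and the serious event listing would accompany it.

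**5. Are the two classes arbitrary?** The neurologic class is not. Section 5.5 singles out cerebral edema, and the open row of Table 4 reads "Events that require discontinuation include and not limited to: Guillain-Barre", continuing with the word syndrome and with encephalitis. Section 6 sets hematologic toxicity apart from all other toxicity in its general rule for withholding treatment. Both classes have a footing in the protocol.

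**The case for a change.** The strongest case for a change is that deriving the overall rate later means choosing an attribution rule after the data are seen. The protocol has two scales. Section 7.7 grades attribution in five levels, one of which is possible. Table 6 asks for yes or no, and its yes describes an event better explained by the drug than by another cause. Section 13.7 does not say which defines relation to treatment. In an open-label single-arm trial, a rule fixed in advance is cleaner, and the cost is one row.

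Part of this stands. The plan names no overall proportion, the two scales differ, and a report of related events should say which it used. It does not amount to a defect, for three reasons.

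- The any-cause overall count needs no attribution rule. It can be shown beside the related count, and an analyst tabulating by both grade and relation would ordinarily do so.
- The objective asks for the toxicity of pembrolizumab. It does not say severe, overall or treatment-related. The complete adverse event summary answers it as written.
- The harm presumes a publication that prints organ rows with no any-event line. Neither Section 13.7 nor the publication plan in Section 14 points to that format.

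The lack of an attribution condition on the two named proportions is also a fair trade-off: it keeps them free of investigator judgment about cause.

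**Conclusion.** The textual observation is correct: only grade 3+ hematologic and grade 3+ neurologic toxicity receive intervals, and no overall severe-event proportion is named. No change to the plan follows. This is a gap in reporting detail that analysts fill sensibly from data the plan already collects and already summarizes by grade and relation. Its size is one table row with an interval of limited precision. At n = 26 the 90% interval is about 11 percentage points wide at 0 events and about 32 points wide at 8 events (16.3% to 48.7%). Type I error (0.0692), power (0.8884), sample size and the progression-free survival rule are all unaffected.

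The conclusion assumes that Section 13.7 is carried out in full, including the all-event summary and the patient-level serious event listing. It also assumes that any related-event figure states which relationship scale it uses. The counts in the illustration are assumed, and the conclusion does not depend on them.
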